### 7.5 Hy's Law

The Hy's Law is used in this study to monitor any possible drug-induced liver injury. The Hy's Law usually means that AST or ALT > 3×ULN and TBiL > 2×ULN, non-biliary increase (usually alkaline phosphatase < 2×ULN) without any other diseases for explanation of the increase. If ALT or AST is > 3×ULN, and TBiL is > 2×ULN without any other previous diseases for explanation of the increase, no matter whether alkaline phosphatase (ALP) increases or not, the Investigator must inform the subject of the central laboratory reports within 48 hours after awareness and ask the subject to return to the study site for central laboratory re-evaluation (if

necessary, re-examinations at local laboratories can be taken). The Investigator conducts re-evaluation and closely monitors or follows-up with the subjects, or stops the study medications according to the Section 4.5.3 Subject withdrawal due to abnormal liver function and Appendix 6: Measures to be Taken for Abnormal Liver Functions in the protocol. The Investigator evaluates the etiology and conducts every essential examination to rule out drug-induced liver injury. If the Investigator confirms the event meets Hy's Law, the event needs to be reported as an SAE.

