### **7.1.1 Serious Adverse Event (SAE)**

SAE is defined as an AE occurring in any period of the study (i.e. run-in, treatment, follow-up) that meets one or more of the following criteria:

1. Resulting in death
2. Immediately life-threatening

The term "life-threatening" refers to an event in which the subject is at immediate risk of direct death at the time of the event. It does not include the situation that might lead to death if it were more severe. For example, drug-induced hepatitis resolved without hepatic failure cannot be considered as life-threatening though it might be fatal.

3. Requiring hospitalization or prolonged hospitalization

Hospitalization or prolonged hospitalization due to elective surgery, routine clinical procedures, social reasons or self-convenience do not need to be recorded as an AE. If the events meet AE criteria e.g., aggravation from previous condition, they should be reported as "serious" or "non-serious" AEs based on routine criteria.

4. Resulting in persistent or significant disability/incapacity
5. Congenital anomaly/birth defect
6. Important medical event: to preclude one of the outcomes listed as above, medical and scientific judgment should be made to assess whether other situations should be considered as serious, such as important medical events that may not be immediately life-threatening or result in death or hospitalization but may jeopardize the subject or may require medical intervention. Examples of such events include allergic bronchospasm requiring intensive treatment in an emergency room or at home; blood dyscrasias or convulsions that do not result in hospitalization; drug dependency or drug abuse, etc.

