### 7.3 SAE Reporting

Once an SAE occurs in the study, the Investigator must immediately take appropriate measures for treatment and report the SAE to the relevant drug administration departments, health administration departments, ethic committees and the Sponsor within 24 hours after awareness. The Investigator needs to ensure the SAE information be recorded on eCRF timely.

When completing the SAE report form (CFDA version), the Investigator must also collect the SAE information requested by the Sponsor. Refer to the Investigator Site File for the details of SAE reporting.

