## 7.5 Hy's Law

The Hy's Law is used in this study to monitor any possible drug-induced liver injury. The Hy's Law usually means that AST or ALT $> 3\times\text{ULN}$  and TBiL $> 2\times\text{ULN}$ , non-biliary increase (usually alkaline phosphatase  $< 2\times\text{ULN}$ ) without any other diseases for explanation of the increase. If ALT or AST is  $> 3\times\text{ULN}$ , and TBiL is  $> 2\times\text{ULN}$  without any other previous diseases for explanation of the increase, no matter whether alkaline phosphatase (ALP) increases or not, the Investigator must inform the subject of the central laboratory reports within 48 hours after awareness and ask the subject to return to the study site for central laboratory re-evaluation (if necessary, re-examinations at local laboratories can be taken). The Investigator conducts re-evaluation and closely monitors or follows-up with the subjects, or stops the study medications according to the Section 4.5.3 Subject withdrawal due to abnormal liver function and Appendix 6: Measures to be Taken for Abnormal Liver Functions in the protocol. The Investigator evaluates the etiology and conducts every essential examination to rule out drug-induced liver injury. If the Investigator confirms the event meets Hy's Law, the event needs to be reported as an SAE.

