## 7.8 Laboratory Safety Assessments

Blood and urine samples are collected for laboratory assessments. The collecting date and time are recorded on the laboratory tests application form. The samples are processed in the central laboratory and the results are reported to study sites within 72 hours.

All subjects are suggested to go to each visit in fasting state between 7:00 am and 10:00 am. The subjects should be informed to avoid heavy physical activities and intake of high fat and high calorie food one day before the visit. Food and beverage except for water are prohibited within 8 hours before the visit. Also, the subjects are informed of not taking the study medications by themselves in the morning of the visit day. Other permitted medications can only be administered with water.

All samples are collected by authorized study staffs, and processed per manuals in the central laboratory. The latest laboratory reference range is provided to study sites during the study. The laboratory results are compared with the reference range values. Results exceeding the normal range are marked. The Investigator evaluates the abnormal results and decides whether they are clinically significant or not.

See Section 7.1.3 for how to record and report AEs relevant to laboratory tests.

The following laboratory safety parameters are measured:

- Hematology: hemoglobin, hematocrit, erythrocytes count, leukocytes count, neutrophils, basophils, eosinophils, monocytes, lymphocytes, and platelet count
- Urinalysis: pH, specific gravity, protein, glucose, erythrocytes, leukocytes, and ketone bodies
- Blood biochemistry: glucose, total bilirubin, ALT, AST, gamma-glutamyl transferase, alkaline phosphatase, albumin, total protein, lactate dehydrogenase, urea nitrogen, creatinine, uric acid, sodium, potassium, chloride, calcium, creatine kinase, creatine kinase isoenzyme, total cholesterol, high-density lipoprotein cholesterol, low-density lipoprotein cholesterol, and triglyceride.

All methods, instruments, and quality control requirements for laboratory tests are described in detail in the manual of central laboratory.

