### **9.3.7 Interim Analysis**

No interim analysis is planned during the double-blind period. Statistical analysis is planned for two stages: 1) Stage 1 is for double-blind period, and 2) Stage 2 is for open-label period. After the completion of the double-blind period, the eligible subjects will enter the open-label period. No alpha sparing or independent data monitoring committee is required in this study.

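### Protocol section 7.5 sets no automatic expedited report for an unconfirmed ALT/AST and bilirubin rise, and words its work-up against its own definition of Hy's Law

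*Supplement*

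**What the plan says.** Section 7.5 of protocol v1.1 uses Hy's Law to watch for drug-induced liver injury. The laboratory signal is ALT or AST above 3×ULN together with total bilirubin above 2×ULN. Hy's Law is met when this occurs "without any other diseases for explanation of the increase".

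When the combination appears with no previous disease to account for it, and whatever the alkaline phosphatase, "the Investigator must inform the subject of the central laboratory reports within 48 hours after awareness" and must ask for a return visit and a repeat test. Monitoring or stopping of study drug then follows section 4.5.3 and Appendix 6. The paragraph goes on: "The Investigator evaluates the etiology and conducts every essential examination to rule out drug-induced liver injury". It closes: "If the Investigator confirms the event meets Hy's Law, the event needs to be reported as an SAE".

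Three other places bear on timing and oversight:

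- Section 7.3 requires an SAE to be reported to the drug and health authorities, "ethic committees and the Sponsor within 24 hours after awareness".
- Section 7.8 says: "The samples are processed in the central laboratory and the results are reported to study sites within 72 hours".
- Protocol section 9.3.7 says: "No alpha sparing or independent data monitoring committee is required in this study". SAP section 3.1 likewise sees no need for such a committee.

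**The concern.** There are two linked faults in one operative safety paragraph.

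The first is about reporting. The combined rise is the event that a sponsor most needs to hear of early, yet section 7.5 makes it reportable only after a judgement that has no time limit. Until then the only clock runs towards the subject. In a trial without an independent monitoring committee, prompt sponsor awareness depends on what the site is told to send.

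The second is about wording. A diagnosis defined by the absence of other explanations is reached by looking for those explanations. An instruction to rule out the drug runs the other way: if it succeeds, the event is not Hy's Law at all. A site that reads it literally could look for reasons to clear the drug, and could leave an asymptomatic case that it attributes to something else as an ordinary adverse event.

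**Working it through.** No statistical figure is involved. The check sets the passages of protocol v1.1 side by side and adds the time limits that they state.

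**1. Does any section make the unconfirmed rise automatically reportable?**

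- Section 7.5: the SAE rule applies on confirmation. There is no notice to the sponsor and no deadline before that. The 48 hours concern the subject.
- Section 4.5.3: lists this combination among the liver criteria for stopping treatment and calls for immediate reporting of SAEs. That duty applies once an event is an SAE. It does not make the combination one.
- Appendix 6, treatment period, item 1: covers this combination and asks for timely recording of AEs or SAEs, with no notice to the sponsor. The 48-hour retest in item 2 is for rises above 3×ULN that do not meet the withdrawal criteria, so it does not cover this combination.
- Section 7.1.1, item 6 (important medical event): "medical and scientific judgment should be made to assess whether other situations should be considered as serious". This route is open before confirmation, but it is discretionary and its examples include no liver finding.
- Section 7.1.3: a clinically significant laboratory abnormality is at least an AE. AEs carry no 24-hour clock.

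So an earlier SAE report is possible, but no section requires one for the laboratory signal alone.

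**2. What do the stated limits add up to?**

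Take one repeat central test, and let SAE awareness start at confirmation:

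- informing and recalling the subject: up to 48 h (section 7.5)
- repeat central laboratory result: up to 72 h (section 7.8)
- SAE report: up to 24 h (section 7.3)

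48 + 72 + 24 = 144 h, and 144 / 24 = 6 days.

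The time until the subject returns and the time for the aetiology work-up come on top, and section 7.5 limits neither. If the first qualifying result were itself reportable, the limit would be 24 h. The 144 h is illustrative. It is no upper bound, because two components are untimed, and no minimum, because a site may act faster or use a local laboratory.

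**3. Is the work-up wording consistent?**

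- Definition in section 7.5: Hy's Law requires that no other disease explains the rise.
- Work-up sentence in section 7.5: the examinations serve to exclude drug-induced injury.
- Section 4.5.3: the cause must be found.
- Appendix 6, list for clarifying the cause: alcohol, other medicines, viral hepatitis A to E, cytomegalovirus and Epstein-Barr virus, autoantibodies and imaging. These are alternative causes, though the list is given for reference only.

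The definition, section 4.5.3 and Appendix 6 agree with one another. The work-up sentence in section 7.5 stands against all three.

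**The case against.** Several stronger readings are tempting, and the documents do not support them.

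- *A reader might infer that the rise can be an SAE only after confirmation, so that 24-hour reporting is absent.* It can become one earlier through hospitalisation, threat to life or the important-medical-event criterion, and a confirmed case has the 24-hour limit. Section 7.5 adds a mandatory trigger. It does not say that an unconfirmed event cannot be serious. Section 7.3 counts from awareness and does not tie awareness to the end of a work-up.
- *A reader might infer that SAE reporting is the only fast channel.* Section 11.2 separately asks the investigator to notify the ethics committee of safety-related SAEs or unexpected AEs, although it gives no deadline. The Investigator Site File, the liver checklist in the investigator's folder and the central laboratory manual are not shown, and any of them might hold an alert procedure.
- *A reader might infer that the whole work-up is misdirected.* The disputed sentence itself begins with evaluating the aetiology, and the sentence before it sends the reader to section 4.5.3 and Appendix 6, where the tests are the right ones for the definition. The fault may be no more than a slip in an English text that is awkward elsewhere.
- *A reader might infer that a late report would alter the liver safety results.* Liver chemistry is measured centrally at every on-treatment visit and summarised under SAP section 9.3.7 whatever the SAE status. A late report delays awareness. It does not remove the laboratory value from the analysis. That SAP section does, however, describe no joint tabulation of aminotransferases with bilirubin.

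One can also hold that assessing the case before applying the Hy's Law label fits a definition by exclusion. That is fair for the label. It does not explain why the sponsor should wait to hear of the signal.

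**Conclusion.** The point holds in limited form. Nothing in protocol v1.1 makes the unconfirmed combined rise automatically reportable to the sponsor. The mandatory report in section 7.5 waits for a confirmation with no deadline, and one sentence of that section contradicts its own definition, section 4.5.3 and Appendix 6.

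The size is a possible delay in sponsor awareness: 144 hours on the stated limits plus two untimed intervals, against 24 hours. This rests on three assumptions: that SAE awareness starts at confirmation, which the documents do not define; that one repeat central test is done; and that the unseen site and laboratory manuals hold no earlier alert. Efficacy results and the planned laboratory summaries are not affected. The change is worth making because it is cheap and concerns subject safety in a trial without independent monitoring.

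**What to change.** Amend section 7.5 in two places.

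- (a) Reconcile the work-up sentence with the definition and Appendix 6, so that its stated aim is to identify or exclude causes other than study drug.
- (b) Require every rise of ALT or AST above 3×ULN with total bilirubin above 2×ULN after the first dose to be reported to the sponsor within the 24-hour limit of section 7.3, counted from awareness of the qualifying laboratory result. One way is to class it as an important medical event under section 7.1.1, item 6. The Hy's Law judgement then follows as an update. The sentence should say whether the first dose means the first run-in dose or the first double-blind dose.

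Treatment and stopping rules stay as written. The cost is two sentences in the protocol and a few extra reports that later prove to have another cause.

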## **7.6 Post-study AE Reporting**

At any time after the study ends, if the Investigator is informed of any AE which is considered possibly related to the study medication, the Investigator needs to promptly report the event to the Clinical Drug Safety department of the Sponsor. The follow-up information of the SAEs after database lock also needs to be reported to the Clinical Drug Safety department of the Sponsor. The contact information is: Email: [[contact]](mailto:[contact]), [contact], [contact].

## **7.7 Lack of Efficacy or Aggravation of T2DM**

The events that are apparently consistent with expected progression of T2DM (e.g., hyperglycemia) do not need to be recorded as AEs. These data is used for efficacy assessment (parameters for glycemic control).

The protocol defines the withdrawal criteria relevant to poor glycemic control/hyperglycemia (see Section 4.5.2 withdrawal criteria due to hyperglycemia and Appendix 4 SMBG Procedures). The Investigator must warrant no other causes for poor glycemic control except for lack of efficacy (e.g. concurrent acute inflammations/infections, and concomitant treatments, etc.). If the disease aggravation is unexpected, it should be reported as an AE. The Investigator is suggested to give the subjects relevant examinations to find out the reason for disease aggravation and record the reason on eCRF.

## **7.8 Laboratory Safety Assessments**

Blood and urine samples are collected for laboratory assessments. The collecting date and time are recorded on the laboratory tests application form. The samples are processed in the central laboratory and the results are reported to study sites within 72 hours.

All subjects are suggested to go to each visit in fasting state between 7:00 am and 10:00 am. The subjects should be informed to avoid heavy physical activities and intake of high fat and high calorie food one day before the visit. Food and beverage except for water are prohibited within 8 hours before the visit. Also, the subjects are informed of not taking the study medications by themselves in the morning of the visit day. Other permitted medications can only be administered with water.

All samples are collected by authorized study staffs, and processed per manuals in the central

laboratory. The latest laboratory reference range is provided to study sites during the study. The laboratory results are compared with the reference range values. Results exceeding the normal range are marked. The Investigator evaluates the abnormal results and decides whether they are clinically significant or not.

See Section 7.1.3 for how to record and report AEs relevant to laboratory tests.

The following laboratory safety parameters are measured:

- Hematology: hemoglobin, hematocrit, erythrocytes count, leukocytes count, neutrophils, basophils, eosinophils, monocytes, lymphocytes, and platelet count
- Urinalysis: pH, specific gravity, protein, glucose, erythrocytes, leukocytes, and ketone bodies
- Blood biochemistry: glucose, total bilirubin, ALT, AST, gamma-glutamyl transferase, alkaline phosphatase, albumin, total protein, lactate dehydrogenase, urea nitrogen, creatinine, uric acid, sodium, potassium, chloride, calcium, creatine kinase, creatine kinase isoenzyme, total cholesterol, high-density lipoprotein cholesterol, low-density lipoprotein cholesterol, and triglyceride.

All methods, instruments, and quality control requirements for laboratory tests are described in detail in the manual of central laboratory.

## **7.9 Physical Examination**

Full physical examination is conducted at each visit except Visit 2, Visit 3 and Visit 16. The physical examination includes a check on: general appearance, head and neck, chest (heart and lung), abdomen, and limbs.

Any finding from physical examination at subsequent study visits is compared with the results at screening visit and is evaluated for clinical significance. See Section 7.1.3 AEs Related to Examinations and Laboratory Tests for how to record and report AEs related to examinations.

## **7.10 12-lead ECG**

A 12-lead ECG examination is conducted at each visit except Visit 2, Visit 3, and Visit 16. The Investigator evaluates the ECG results and records the results on eCRF as “normal” or “abnormal with/without clinical significance”. See Section 7.1.3 AEs Related to Examinations and Laboratory Tests for how to record and report AEs related to laboratory examinations.

## **7.11 Vital Signs**

Vital signs (blood pressure, pulse rate, respiratory rate and body temperature) are measured according to study protocol. Height and body weight are included as part of vital sign assessments.

The subjects should rest for at least 5 minutes before vital sign assessments. Throughout the study, all efforts are made to measure pulse rate, respiratory rate and blood pressure from the same arm. The arm used for measurement is documented in the original records.

### **Pulse rate**

Palpation on the radial artery is suggested to last for at least 30 seconds to calculate the number of beats per minute, which is recorded on eCRF. If necessary, palpation is on bilateral radial artery simultaneously to check the symmetry. It is recommended to be marked on eCRF if there is any asymmetry.

### **Body temperature**

A thermometer is placed at deep axillary region of the subjects. The subjects are told to hold the thermometer tightly and read the temperature 10 minutes later. Be noted that there should not be heating or cooling objects at the axillary region and sweat at the axillary region should be swiped.

### **Respiratory rate**

The subjects are observed for breathing rhythm and breathing frequency per minute is recorded.

### **Blood pressure**

A mercury sphygmomanometer is used for measuring blood pressure. The subject should be in a quiet place with his feet flat on the floor back against the chair. Cigarettes and coffee is prohibited and bladder is emptied within 30 minutes before the assessment. The subject's upper arm is exposed and stretched slightly with the elbow at the same height with heart. The cuff is closely and evenly wrapped around upper arm with its lower edge at about 2.5 cm above the antecubital fossa and the center of cuff at the surface of brachial artery. After touching the brachial artery, the examiner puts the stethoscope's bell over the brachial artery for auscultation. Then the cuff is inflated while auscultation. After the sound of brachial artery pulse disappears, the cuff continues to be inflated until the reading values increase for additional 30 mmHg. Then the cuff is deflated gradually (2–6 mmHg/s). Eyes are kept at the same level with the mercury gauge while the mercury column is descending, and blood pressure is read according to auscultation. Blood pressure is measured at least twice with two-minute interval and the average of the two measurements is calculated. If the difference of the two measurements in systolic or diastolic blood pressure is larger than 5 mmHg, a third measurement is done after 2 minutes and the average of 3 measurements is calculated.

### **Height and Weight**

Shoes and thick clothes should be taken off while height and body weight are being measured. The brand and model of the scales used for body weight measurement in each site should be kept the same throughout the study.  $BMI = \text{Body Weight (kg)} / \text{Height (m)}^2$ .

## 7.12 Pregnancy

The subject who becomes pregnant while receiving the study medication must immediately discontinue the study medication. Pregnancy itself is not considered as an AE, but it must be reported on the pregnancy form and submitted to the Sponsor as special safety information. The reporting time limit is the same as SAE reporting. All pregnancies must be followed up until the pregnancy outcome is obtained (e.g. spontaneous abortion, selective termination, ectopic pregnancy, full term birth, congenital anomaly). In addition, if a male subject's partner is pregnant during the study, it is also reported to the Sponsor and followed up until pregnancy completion.

Congenital anomaly, birth defects and spontaneous abortion should be reported as SAEs. Artificial abortion without complications do not need to be recorded as AEs. The pregnancy outcomes after database lock should be reported to the Clinical Drug Safety department of Sponsor. The contact information is: Email: [[contact]](mailto:[contact]), [contact], [contact]. Pregnancy report form refer to ISF.

